1	
2	
3	
4	
5	INTERMITTENT EXOTROPIA STUDY 5
6	(IXT5)
7	
8	
9	A Randomized Clinical Trial of Overminus
10	Spectacle Therapy for Intermittent Exotropia
11	
12	
13	
14	
15	
16 17	PROTOCOL
18	
19	
20	
21	
22 23	Version 3.0
23 24	November 22, 2019
25	
26	
27	
28	
29 30	
31	

PROTOCOL AMENDMENT II (11-22-19)

35 No

Note that changes to the original (18-month) protocol (protocol changes #1 through #5) are incorporated throughout the protocol. The 18 to 36 month extension study protocol (protocol change #6) is detailed at the end of this protocol amendment II.

Protocol Change #1 – Discontinue weaning overminus lens treatment between 12-15 months

Original Protocol

A three-month period of weaning of overminus consisted of prescribing the overminus group subjects -1.25D overminus (half of the -2.50D prescribed at randomization) at the 12-month visit and wearing this correction until discontinuing the overminus completely at the 15-month visit. The purpose of weaning overminus as opposed to discontinuing overminus abruptly was to potentially help retain the effect of the overminus off treatment.

Changed Protocol

At the 12-month visit, subjects in the overminus treatment group will have overminus treatment discontinued immediately, without weaning. These subjects will be prescribed the non-overminus spectacles they would have been prescribed at 15 months in the original protocol (section 2.6.1).

The flow chart in section 1.17 has been updated. Section 4.3.2 on risks of overminus was also updated.

Relevant additions to the analysis plan:

• Because weaning may increase the retention of the treatment effect once off treatment, discontinuing the weaning may decrease the off-treatment effect observed at 18-months. For this reason, the 18-month off-treatment analyses will be performed using 1) the full cohort, and 2) a cohort limited to subjects who were prescribed weaning between 12 to 15 months (i.e., prior to weaning being discontinued per Protocol Amendment II) (see modifications to section 5.2).

• In addition, 18-month distance control and change from baseline will be tabulated by treatment group according to prescribed weaning status (i.e., full, partial, or no prescribed weaning) (section 5.3.2.2).

Rationale

The Data Safety Monitoring Committee (DSMC) concluded on 10/25/19 that progression of myopia is occurring more frequently in subjects treated with overminus spectacles compared to non-overminus spectacles. Between baseline and 12 months, the mean change in spherical equivalent refractive error at 12 months was -0.42 D (diopter) in the overminus group and -0.05 D in the non-overminus group (difference = 0.39 D P = <.0001). The proportion of subjects whose spherical equivalent refractive error changed by more than 1.00D was 17% in the overminus group (29 of 168); and 2% in the non-overminus group (3 of 146). The DSMC recommended that all subjects active in the full treatment* or weaning phases in both treatment groups be asked to come in for a visit as soon as possible to be given the new information, complete their pending follow-up visit, receive study-paid non-overminus glasses (regular

glasses or no-correction glasses) to be worn through 18 months, and be invited to continue in the study after 18 months to be treated at investigator discretion and to return for visits at 24 and 36 months.

82 83 84

85

86

87

80

81

*Note that the protocol does not require amending the 0 to 12-month on-treatment period in order to discontinue full overminus treatment given that the 37 remaining 12-month visits (as of 11/5/19) were planned to occur by December 2019. These 12-month visits will be completed only slightly early (all subjects have ≥9 months of treatment). As detailed above, non-overminus glasses will be prescribed between 12 and 18 months.

88 89 90

Protocol Change #2

91 92

Original Protocol

93 94 A lens change was required at the 15-month visit in both treatment groups to allow for discontinuation of half-strength (-1.25D) overminus spectacles in the overminus group. The 15-month glasses prescription is the same as the non-overminus group has received throughout the protocol.

95 96 97

Changed Protocol

98 99 100

The 15-month spectacle prescription is the same as in the original protocol (i.e., non-overminus for both treatment groups), but whether a patient needs to receive a change in spectacles at 15 months to achieve this prescription depends on whether their spectacles had been changed to non-overminus at the 12-month visits occurring after Protocol Amendment II.

101 102 103

Section 2.6.1 on treatment in the **overminus** group has been revised as follows:

104

108

109

110

111

112

15-Month*

105 106 107

- If the 12-month spectacles for a subject were issued **before** Protocol Amendment II and therefore contain partial-strength overminus (-1.25D), they should be changed to nonoverminus lenses at the 15-month visit to discontinue the overminus treatment.
- If the 12-month spectacles for a subject were issued **on/after** Protocol Amendment II and therefore are already non-overminus spectacles, the non-overminus spectacles should be continued at the 15-month visit.

*Unless the subject has already met deterioration criteria confirmed by masked examiner as described in section 3.7, in which case spectacles are prescribed at investigator discretion.

113 114 115

Section 2.6.2 on treatment in the **non-overminus** group has been revised as follows:

116 117

121 122

123

124

125

15-Month*

- 118 • If the 12-month spectacles for a subject were issued **before** Protocol Amendment II and, the 119 non-overminus lenses should be replaced with new non-overminus spectacles at the 15-120 month visit, to maintain masking of treatment groups.
 - If the 12-month spectacles for a subject were issued on/after Protocol Amendment II and therefore are already non-overminus spectacles, the non-overminus spectacles should be continued at the 15-month visit. There is no longer a reason to change the glasses to maintain masking, given that both treatment groups would already be wearing nonoverminus glasses in this situation.
- 126 *Unless the subject has already met deterioration criteria confirmed by masked examiner as 127 described in section 3.7 in which case spectacles are prescribed at investigator discretion.

128 129 Rationale for Change 130 Whether glasses need to be changed at 15-months depends on when each subject's 12-month glasses 131 were issued, before or on/after Protocol Amendment II. See details in changes to protocol (above). 132 133 **Protocol Change #3** 134 135 Original Protocol 136 Cycloplegic refraction and autorefraction were not performed at the 18-month visit. 137 138 **Changed Protocol** 139 Cycloplegic refraction will be performed at the 18-month visit, and autorefraction will be mandatory if 140 an autorefractor is available at the site (section 3.4). Analysis of 18-month refractive error data was 141 added to section 5.4.1. 142 143 Rationale for Change 144 Given the increased myopia progression in the overminus lens group, the 18-month visit is the first 145 opportunity to assess whether the overminus group continues to have higher myopia than the non-146 overminus group or whether the two treatment groups start to become similar once treatment is discontinued. 147 148 149 **Protocol Change #4** 150 151 Original Protocol 152 Cycloplegic axial length and additional biometry were not measured in the study. 153 154 **Changed Protocol** 155 Cycloplegic axial length, flat corneal radius, anterior chamber depth, and lens thickness (if available) will be measured at 18-months (section 3.4). Analyses for this data are described in 156 section 5.3.1.5 and 5.3.1.6 157 158 159 Rationale for Change 160 Given the increased myopia progression in the overminus lens group, the study is interested in whether 161 axial length also differs between treatment groups. 162 163 **Protocol Change #5** 164 165 Original Protocol Study-paid spectacles (lenses and frame) were provided at the 12-month visit and a change of 166 lenses was provided at the 15-month visit. 167 168 169 Changed Protocol 170 Study-paid spectacles (frames and lenses) will be provided at 12 months, 15 months and 18 months 171 (section 4.7) 172 173 Rationale for Change 174 Paying for a full set of spectacles at the 15-month visit will enable the study to offer a full set of spectacles to all patients coming in for early visits to have treatment discontinued. Study-paid 175

IXT5 Protocol v3.0 (11-22-19)

spectacles will be provided at 18 months now that cycloplegic refraction is being performed to check the spectacle prescription at that time.

178 179

Protocol Change #6

180

- 181 Original Protocol
- The study ends with the 18-month visit.

183

- 184 Changed Protocol (also see next page)
- This Protocol Amendment allows for an extended follow up period from the 18 to 36 months after randomization. All patients enrolled in IXT5 will be invited to participate, regardless of whether they are still active in the 18-month study. *See specifications on next page*.

188

- 189 Rationale for Change
- 190 Given the higher rate of myopia progression observed in overminus group vs. non-overminus group
- between randomization and 12 months, the goal is to determine whether the overminus group
- 192 continues to have higher myopia than the non-overminus group or whether the two treatment groups
- will have similar myopia progression over the long term.

PROTOCOL AMENDMENT II (11-22-19) PROTOCOL CHANGE #6 (CONTINUED) EXTENDED FOLLOW UP BETWEEN 18 TO 36 MONTHS

196 197 198

195

This protocol change allows for an extended follow up period 18 to 36 months after randomization.

199 200 201

202

Objective

To compare long-term refractive error between subjects originally treated with either overminus spectacles or non-overminus spectacles as part of the 18-month randomized trial.

203204205

Protocol Specified Follow-up Visits

Visits will occur at 24 months (±3 months) and 36 months (±3 months) from randomization.

206207208

209

210211

213

214

215

216

217

218219

220

221

223

224

225226

227

228229

230

231232

235

236

237

238239

Study Procedures/Data Collection

- The following testing procedures will be performed in the following order: using similar methods as the 18-month visit except where noted.
- 1. Treatments used since the last visit
- 212 2. Visual acuity
 - Measured using the investigator's usual testing procedure using an optotype method.
 - Testing must be performed in current refractive correction.
 - If prism is currently prescribed, visual acuity testing should be performed with prism.
 - If deliberate overminus* is currently prescribed, visual acuity testing should be performed *with* the overminus correction.
 - If visual acuity is 20/32 or worse (75 letters or less) in either eye, a manifest refraction must be performed. If the examiner believes that the patient's current correction is not optimal, trial frames with new correction should be used for all testing at the visit. This includes testing visual acuity again, with the patient wearing trial frames.
- 222 3. Control of the Exodeviation #1 masked
 - Testing must be performed in current refractive correction.
 - If prism is currently prescribed, testing should be performed *without* prism.
 - If deliberate overminus** is currently prescribed, testing should be performed in trial frames *without* the overminus component of the prescription.
 - 4. Stereoacuity Testing **masked** stereoacuity is tested only once, with no repeat testing on the same day or a subsequent day.
 - Testing must be performed in current refractive correction.
 - If prism is currently prescribed, stereoacuity testing should be performed with prism.
 - If deliberate overminus** is currently prescribed, stereoacuity testing should be performed *with* the overminus correction.
- 5. Control of the Exodeviation #2 masked see details under Control Testing #1 above
- 234 6. Cover Test and PACT Testing masked
 - Testing must be performed in current refractive correction.
 - If prism is currently prescribed, ocular alignment testing should be performed *without* prism.
 - If deliberate overminus** is currently prescribed, ocular alignment testing should be performed in trial frames *without* the overminus component of the prescription.
- 7. Control of the Exodeviation #3 - masked see details under Control Testing #1 above

- 241 8. Assessment of Deviation Throughout Exam- masked
- 242 9. Cycloplegic Refraction
- 243 11. Cycloplegic Autorefraction (mandatory if autorefractor is available at the site) as described in section 3.4
- 12. Cycloplegic Axial Length Measurement and Additional Biometry (mandatory if biometer is
 available at the site) as described in section 3.4
 - Axial length

247

248

249

251

255256

257258259

262263

264

265266

267268269

270271

272273

274

275

276277

278

279280

283

284

285 286

287

- Flat corneal radius
- Anterior Chamber depth
- Lens thickness, if available

*Deliberate overminus lenses = lenses that yield > 0.50 D *more minus* spherical equivalent (SE) than the refraction SE. Note that prescribing underplus or no plus is not considered deliberate overminus.

Steps #3 through #8 must be performed in order by a masked examiner who is a pediatric ophthalmologist, pediatric optometrist, or certified orthoptist.

Treatment

After 18 months, IXT treatment (surgical, non-surgical, management of refractive error) is at investigator discretion.

Costs

The parent/guardian of each subject will be compensated \$50 for completion of each of the 24-month and 36-month visits, up to a total of \$100. If there are extenuating circumstances, and the subject is unable to complete the annual study visits without additional funds due to travel costs, additional funds may be provided.

The study will pay for visits specific to the research study, but will not pay for usual care visits that would occur whether or not the subject was in the study. The cost of usual care visits will be the responsibility of the subject or his/her insurance company.

The study will pay for a pair of spectacles (lenses and frames) at the first extension study visit (24 months or 36 months). Spectacle changes / new spectacles prescribed at other times will not be paid for by the study.

Treatment after 18-months is at investigator discretion and is not part of this protocol. Any costs associated with treatment will not be paid for by the study.

Risks

The procedures in this study are part of daily eye care practice in the United States and pose no known risks.

Subject Contact During Follow Up

Between annual visits, subjects may be called periodically by the Jaeb Center to promote retention.

Re-consenting of Subjects

An addendum to the original informed consent form (and addendum to the assent form, if required) for the extension study will be signed by parents who elect to continue their child's study participation. Re-consenting will occur at the next 12, 15, or 18-month randomized trial visit but could occur at other times either before or after participation in the 18-month trial has ended. A subject (and respective parent) may withdraw from the study at any time.

294295 Statistical Analyses

The following analyses will be completed separately at the 24-month and 36-month visits to evaluate the effect of the overminus treatment approach followed by usual clinical care versus the non-overminus treatment approach followed by usual clinical care:

- Spherical equivalent refractive error will be compared between treatment groups using an ANCOVA model that adjusts for baseline spherical equivalent refractive error. The treatment group difference and a 95% confidence interval will be calculated.
- Mean distance control (average of 3 measurements) will be compared between treatment groups using an analysis of covariance (ANCOVA) model, which adjusts for baseline distance control, distance PACT, age, refractive error, and use of ADHD medication, to address potential residual confounding.
- The proportion of subjects with no spontaneous tropia will be compared between treatment groups as in section 5.1.2.1.
- Axial length, flat corneal radius, anterior chamber depth, and lens thickness (if available) will be compared between treatment groups as in section 5.3.2.3 and
- Secondary outcomes of near control, angle magnitude, and near stereoacuity will also be compared between treatment groups as in section 5.3.1.
- Treatments used since the last visit will be tabulated by treatment group.

	PROTOCOL AMENDMENT I (11-8-16)
]	This amendment provides for the following protocol changes:
]	Protocol Change #1
r	Original Protocol At the time of enrollment and each follow-up visit at 6, 12, 15, and 18 months, parents are asked to respond to a survey of symptoms potentially associated with spectacle treatment (headaches, eye strain, and other problems with spectacle wear) based on their observations of their child in the past weeks.
(Changed Protocol
1	 To add a 7-question survey of intermittent exotropia symptoms to be administered to the child. To add a health-related quality of life questionnaire to evaluate whether either treatment impacts the effect of intermittent exotropia on quality of life.
	• Children ages 5 and older at the time of enrollment will complete an 11-item questionnaire to assess how their eye condition affects their quality of life. Children years of age and younger at the time of enrollment will not complete the child questionnaire.
	 A 16-item parental questionnaire will assess how the child's eye condition affects the quality of life of the parent (for all subjects).
3	3. The surveys and questionnaires will be completed at the time of enrollment; and at 6-month, 12-month, and 18-month follow-up visits.
	Rationale for Change There is value in determining how overminus treatment may impact the child's intermittent exotropia symptoms and the child's and parent's quality of life. Recently, a patient derived 7-question intermittent exotropia symptom survey has been developed for childhood IXT and, previously, a patient and parent derived HRQOL instrument has been developed specifically for XT and used successfully in previous PEDIG IXT studies.
I	Protocol Change #2
I	Original Protocol Both the 12-month on-treatment comparison of mean distance control and the 18-month off-reatment comparison of mean distance control are considered separate primary analyses, with each allocated 0.05 alpha.
t	Changed Protocol The 12-month on-treatment comparison will be the sole primary analysis and the 18-month off- reatment comparison changed to a planned secondary analysis upon which sample size continues to be based.
	Rationale for Change The previous allocation of 0.05 alpha to both the 12-month on-treatment comparison and the 18-month off-treatment leads to an experiment-wise alpha of up to 0.10. Selecting one comparison

as the primary analysis limits the experiment-wise alpha to no more than 0.05. Whether

2

360

overminus spectacles can improve control of exotropia after 12 months of treatment is the primary study question. The 18-month off-treatment analysis can be considered the secondary question. First, the overminus weaning schedule may require refinement before we can definitively determine the effect of overminus after treatment is discontinued. Second, an ontreatment effect would need to be seen at 12 months in order to potentially see an effect off-treatment at 18 months. Finally, clinicians who use overminus to delay another form of treatment, such as surgery, may be less interested in the off-treatment effect. Whether a benefit of overminus can be maintained off treatment, will still be addressed by the 18-month off-treatment comparison as a planned secondary analysis.

Protocol Change #3

Original Protocol

The primary analysis uses_the observed 12-month visit data regardless of whether non-randomized treatment was prescribed. Subjects who are lost to follow up before the 12-month visit are excluded. The 18-month off treatment analysis was defined similarly.

Changed Protocol

The primary analysis (section 5.1) will be defined as follows:

- Subjects who are treatment crossovers (non-overminus group subjects who are prescribed overminus therapy; overminus group subjects who have overminus spectacles formally discontinued) will have their observed 12-month data analyzed provided they complete at least one distance control testing at the 12-month outcome exam; otherwise their average distance control score will be imputed using multiple imputation.
- Subjects who are prescribed IXT treatment *other than overminus or non-overminus refractive correction* (e.g. surgery, vision therapy, patching) will have their average distance control score imputed using multiple imputation, using data from all visits prior to the initiation of the alternative therapy. Multiple imputation will be used for these subjects regardless of whether any control testing is completed at the 12-month visit.
- Subjects who are lost to follow up before the 12-month visit will also have their outcome imputed using multiple imputation.

The original primary analysis is now an alternative analysis in section 5.1.1.1, along with the original alternative analysis. A third alternative analysis has been added to explore the effect of how treatment crossovers are handled in the primary analysis.

The secondary 18-month off-treatment analysis was changed in parallel (section 5.2).

Rationale for Change

For subjects who are prescribed treatment other than what they were randomized to (e.g. surgery, overminus spectacles, vision therapy) the 12-month visit data would reflect the effect of the non-randomized treatment they receive. If a higher proportion of subjects in the non-overminus group are prescribed a non-randomized treatment that is more effective than the overminus spectacles, the study might fail to detect an effect of overminus, if one exists. It was felt acceptable and conservative to analyze the observed 12-month data for treatment crossovers given that these subjects are receiving study treatments; however, it was felt appropriate to impute 12-month data using multiple imputation for subjects who are prescribed IXT treatment other than overminus or non-overminus refractive correction (e.g. surgery, vision therapy,

patching), an approach which would not be expected to bias the analysis either toward or against a treatment effect of overminus (although any procedure for handling of this issue has some potential for bias). A similar rationale applies to the 18-month off-treatment analyses.

413 414

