3.3 Masking of Treatment Group

Subjects will be masked to treatment group throughout the study. Subjects who do not have refractive error that requires correction (*see sections 2.6.1 and 2.6.2*) will be prescribed plano lenses if randomized to the non-overminus group.

1298 1299 1300

1301

1302

1303

1304

1305

Key outcome testing at each follow-up visit (*see section 3.3.1*) will be performed by an examiner masked to treatment group. Although the examiner will see the subject's spectacles during test, the presumption is that treatment group is unlikely to be discerned because 1) all subjects will be wearing spectacles and 2) because both treatment groups will have a range of prescriptions depending on subjects' underlying refractive error in addition to whether an overminus component is included. The Masked Examiner must be a pediatric ophthalmologist,

pediatric optometrist, or certified orthoptist. The Masked Examiner should preferably be someone *other than* the investigator.

If necessary at rare sites, the Masked Examiner may be the investigator if the investigator remains masked to the randomized treatment. At such sites, for prescription of spectacles throughout the study, the investigator should sign two prescriptions (one overminus prescription and one non-overminus prescription), after which an unmasked coordinator would provide the parent with the appropriate prescription according to the subject's treatment group.

 The investigator will be unmasked to treatment group except at rare sites in which he/she must serve as the masked examiner. The investigator should not discuss a subject's treatment group with the subject or his/her parents.

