 - 10. Assessment of Deviation Throughout Exam (Masked)

1407 1408

The following procedures should be performed by either the Masked Examiner or another study-certified examiner:

14101411

1409

1412

1413

1414

1417

14181419

1420

1421

1422

1423

1424

- 11. Distance Visual Acuity Testing: Monocular distance visual acuity testing with the habitual correction and without cycloplegia will be measured using the same testing procedure as used for enrollment. Visual acuity may be tested at the start of the exam or before the cycloplegic refraction.
- 1415 12. Cycloplegic Autorefraction (12-month and 18-month visits only, mandatory if autorefractor is available at the site)
 - Refractive error must be measured with the same autorefractor used at enrollment following cycloplegia with 1% cyclopentolate (see cycloplegic refraction below).
 - If cycloplegic autorefraction was completed at enrollment, then it must be measured with the same autorefractor used at enrollment.
 - Regardless of whether cycloplegic autorefraction was completed at enrollment, it is mandatory to measure cycloplegic autorefraction if an autorefractor is available at the site.
 - Recorded values will be based on a single measurement by the instrument (which may be a mean of several individual measures depending on system)
- 1426 13. Cycloplegic Axial Length Measurement and Additional Biometry (18-month visit only) (see manual of procedures).

• Axial length

1433 1434

1435

1436

14371438

1439

14401441

1442

1443

1444

1445

1446

1447 1448

1449 1450

1451

14521453

1454

1455

1456

14571458

1459

1460

1461

1462

1463 1464

1465

1466

1467 1468 1469

1471

- Flat corneal radius
- Anterior Chamber depth
- Lens thickness, if available
- 1432 14. Cycloplegic Refraction (12-month and 18-month visits)
 - A cycloplegic refraction will be performed at the 12-month and 18-month visits. The cycloplegic refraction will be performed regardless of whether a cycloplegic autorefraction is performed.
 - Cycloplegic refraction is performed 30 to 45 minutes following at least one application of cyclopentolate 1% per investigator's usual dosage and timing routine.
 - The cycloplegic refraction is based on cycloplegic retinoscopy, which may be done with glasses off or as an over-refraction in front of the current spectacles. Subjective refraction is allowed.

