5.4.4. No Spontaneous Tropia

The proportion of participants with no spontaneous tropia (defined in section 4.1.1) will be reported for each treatment group at 24-months and 36-months.

796 **5.4.5. Angle Magnitude by PACT**
797 At the 24- and 36-month time points, the distribution of the magnitude of the deviation by
798 Prism Alternate Cover Test (PACT) will be tabulated by treatment group. This will be
799 completed separately at distance and at near.

800
801 **5.4.6. Stereoacuity**
802 At the 24- and 36-month time points, the distribution of the near stereoacuity by testing
803 with the Preschool Randot Test will be tabulated by treatment group.

804
805 **5.4.10 Cycloplegic Autorefraction at 24 and 36 Months**
806 The change from baseline in cycloplegic autorefraction will be tabulated for each
807 treatment group and descriptive statistics will be calculated at 24- and 36-months for
808 participants who have these data (autorefractors are not available at all sites). The
809 magnitude of refractive error (as determined by autorefraction) will be tabulated by
810 treatment group and descriptive statistics will be calculated.

811
812 **5.5 Additional Tabulations**

813
814 **5.5.1 Development of Esodeviation**
815 The number and percent of participants with an esodeviation at 24 months and 36 months
816 will be tabulated by treatment group. The magnitude of the esodeviation (by PACT) and
817 whether it was a constant tropia, intermittent tropia, or a phoria will be specified.

818
819 **5.5.2 Reduction of Distance Visual Acuity**
820 Any cases of reduced visual acuity of ≥ 2 logMAR lines from baseline in either eye when
821 wearing best refractive correction will be tabulated by treatment group.

822
823 **5.5.3 Additional Treatment**
824 Any additional treatment used after 18 months was at investigator discretion and will be
825 reported by treatment group. At the 24- and 36-month visits, treatments used since the
826 last visit will be tabulated according to treatment group.

827
828 **5.5.4 Tabulations by Baseline Refractive Error Subgroups**
829 Summary statistics for refractive error at 24 and 36 months will be tabulated by baseline
830 refractive error subgroups for each treatment group. Baseline refractive error groups will
831 be defined as follows: myopic (-0.50D to -6.00D SE), emmetropic (-0.375D to +0.375D
832 SE), and hyperopic (+0.50D to +1.00D SE). Additionally, biometric measures (Section

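### The 18 to 36 month extension exists to compare refractive error, but its masking requirement stops one step short of the cycloplegic refraction; masking that step where possible, and showing autorefraction beside it, is a cheap improvement

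*Protocol*

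**What the plan says.** **Objective.** Protocol Amendment II, Change #6, gives one objective for the extension: "To compare long-term refractive error between subjects originally treated with either overminus spectacles or non-overminus spectacles". The first analysis listed there is an ANCOVA of spherical equivalent at 24 and 36 months, adjusted for its baseline value.

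**Masked block.** The extension procedures state: "Steps #3 through #8 must be performed in order by a masked examiner". Each of those steps also carries its own masked label. The next item, "9. Cycloplegic Refraction", lies outside the range and has no label.

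**Who may refract.** The extension follows methods similar to the 18-month visit. For visual acuity, autorefraction, biometry and refraction, Protocol 3.4 says: "The following procedures should be performed by either the Masked Examiner or another study-certified examiner". Protocol 3.3.1 does not list refraction among the masked tests. Protocol 3.3 says: "The investigator will be unmasked to treatment group except at rare sites".

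**How it is measured.** Protocol 3.4 bases the value on retinoscopy, "which may be done with glasses off or as an over-refraction in front of the current spectacles", and permits subjective refraction. With over-refraction, the recorded value is spectacle power plus over-refraction.

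**Device-based measures.** At 24 and 36 months, cycloplegic autorefraction and axial length with other biometry are mandatory where the site has the device. SAP 5.4.10 says: "The change from baseline in cycloplegic autorefraction will be tabulated for each" treatment group. The opening paragraph of SAP 5.4 adds that every outcome in that section gets a between-group difference with 95% CI and no p-value, using a baseline-adjusted ANCOVA for continuous outcomes. SAP 5.3 makes biometry the extension's secondary analysis, with p-values adjusted for false discovery rate.

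**The concern.** Protocol 3.3 sets the principle that key outcome testing is done by someone who does not know the arm. When Amendment II made refractive error the objective of a new follow-up period, the masked block kept its earlier content: control, stereoacuity and alignment. At 24 and 36 months SAP 5.4 treats those as exploratory.

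Three features make an unmasked refraction vulnerable:

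- The endpoint of retinoscopy, with or without subjective refinement, depends on examiner judgement.
- The person refracting may know the arm.
- Expectation now has a direction. The amendment rationale and Protocol 4.3.2 both report more myopic progression with overminus, and the DSMC asked that families of subjects still in treatment or weaning be told.

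The extension asks whether the arms stay apart or become similar. The answer may turn on a small residual difference, where a slight average tilt in measurement matters most. A persisting difference could be challenged as expectation.

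**Working it through.** **1. Passages side by side (24 and 36 months).**

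| Measurement | Role | Masked examiner required? |
|---|---|---|
| Control, stereoacuity, alignment (steps 3 to 8) | Exploratory (SAP 5.4) | Yes |
| Cycloplegic refraction (step 9) | Sole stated objective | No |
| Cycloplegic autorefraction | SAP 5.4: difference and CI, no p-value | No, but instrument-read; only where available |
| Axial length and biometry | Secondary (SAP 5.3); no baseline value | No, but instrument-read; only where available |

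The gap is in the text. Masked refraction is allowed but not required.

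**2. Could this explain the 12-month signal?** Inputs from Amendment II, Change #1 rationale: mean change -0.42 D against -0.05 D, stated difference 0.39 D, P<.0001; change above 1.00 D in 29 of 168 against 3 of 146.

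- Reproducing the proportions: 29/168 = 17.3% and 3/146 = 2.1%, matching the stated 17% and 2%. The difference is 15.2 points (95% CI 9.0 to 21.4); Fisher p = 3 × 10⁻⁶.
- The crude difference in means is 0.42 − 0.05 = 0.37 D, against the stated 0.39 D. The text does not say whether 0.39 is adjusted, so both are used below.
- Assume the same 168 + 146 subjects, hence 312 degrees of freedom. A two-sided P of .0001 corresponds to t = 3.94, so SE ≤ 0.39/3.94 = 0.099 D, or 0.37/3.94 = 0.094 D.
- The lower 95% limit is then at least 0.39 − 1.968 × 0.099 = 0.20 D, or 0.37 − 1.968 × 0.094 = 0.19 D.
- For the proportions, the overminus count would have to fall from 29 to 12 before Fisher p passed 0.05 (p = 0.060 at 12; 0.036 at 13).

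An average between-arm shift of at least about 0.19 D would be needed to remove significance at 12 months.

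**3. What a smaller tilt could do in the extension.** Neither the tilt nor the 24/36-month SE is in the documents; both are assumed. With no true difference, the rejection rate at nominal 5% is P(|Z + tilt/SE| > 1.96).

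| Assumed tilt | Share of 0.39 D | SE 0.07 D | SE 0.12 D |
|---|---|---|---|
| 0 | 0% | 5% | 5% |
| 0.10 D | 26% | 30% | 13% |
| 0.15 D | 38% | 57% | 24% |
| 0.20 D | 51% | 82% | 39% |

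The table shows sensitivity only. It does not show that any tilt exists.

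**4. Can the lenses reveal the arm?** Under Protocol 2.6.1 and 2.6.2, the overminus group wears -2.50 D overminus up to the 12-month visit, so an over-refraction then can reveal the arm. By 18 months both groups should be in non-overminus lenses. After 18 months correction is at investigator discretion. The lens route is mainly a 12-month matter; in the extension the issue is who refracts and what that person knows.

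**The case against.** The strongest reply is that device-based checks are already planned.

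- **Autorefraction.** From SAP 5.4.10 alone a reader might infer that it is merely tabulated at 24 and 36 months. The opening rule of SAP 5.4 does not support that: a baseline-adjusted difference with 95% CI is due. At 12 and 18 months SAP 4.1.9 repeats the refractive-error comparison separately for autorefraction. This stands, and it reduces the SAP change to status and placement.
- **Biometry.** It is a formal secondary analysis, and SAP 5.3 also correlates it with refractive error. This stands too, although without a baseline it cannot show progression since randomization. Both safeguards depend on device availability.
- **Over-refraction.** A reader might infer that refracting over study spectacles unmasks the extension. It does not: arm-specific lenses are gone by then. At 12 months the route is real, but only 37 such visits remained on 11/5/19, and earlier ones preceded the amendment's disclosure.
- **Who refracts.** A reader might infer that the unmasked investigator normally does so. The documents say only that the investigator is usually unmasked and that the Masked Examiner or another certified examiner may refract.
- **Side effect of masking refraction.** Masked examiners see the spectacles. One who refracts a child still in overminus could infer the arm and carry that into later control testing. This stands and shapes the fix.

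**Conclusion.** The point holds as a cheap improvement. The extension's sole stated objective rests on a judgement-dependent measurement for which masking is optional, in a setting where the arm is often known and the expected direction has been published to sites. The safeguards are real but partial. The result is a risk of detection bias of unknown size; nothing in the documents shows that bias occurred.

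Two stronger readings should be resisted. The first is that the 12-month myopia finding, and the DSMC's action on it, may be a measurement artefact. The needed shift of about 0.19 D or more, and the 29 against 3 split, make that an unlikely sole explanation. The second is to quote an inflated false-positive rate as a property of this trial. Those rates are correct arithmetic on assumed inputs and move with them.

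One limit: the SAP text immediately before 5.2.1 was not available to this review. The exact 24/36-month primary model, its refraction source and any masking provision there could not be checked. The protocol procedures that sites follow contain no requirement for masked refraction.

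**What to change.** 1. **Protocol, Change #6.** Extend the masked block to step 9 where the masked examiner already present is qualified to refract. Do it after all masked control and alignment testing, and with glasses off. Glasses-off also avoids a practical conflict: over-refraction needs the lens power, while Protocol 3.3.1 bars the Masked Examiner from lensometry.
2. **CRF.** Record whether the person refracting was masked to arm.
3. **SAP.** Name the 24/36-month autorefraction ANCOVA as a sensitivity analysis reported beside the primary refractive-error comparison, and show the primary result by refractor masking status as well.
4. **Visits with later control testing still to come.** Where available, a different examiner already on site and not told the arm should refract, so that the control examiner is not unmasked.

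**Cost.** Procedure wording, one CRF item, and a change in the status and placement of an analysis already planned, plus one breakdown. No visit or test is added. Some masked examiners, for example certified orthoptists, may not refract; at those sites the flag and the autorefraction analysis carry the check. A separate masked refractor at every site would need extra staff and is not proposed. If visits are already complete, the autorefraction analysis can still be reported in this way, with disclosure of who refracted as far as it is known.
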